8.3.2 Formulation of Control Product

Safeway Pharmacy will make matching placebos capsules using the same gelatin capsules and microcrystalline cellulose filler. They will be visually indistinguishable from the over-encapsulated Nature's Bounty melatonin product.

8.3.3 Packaging and Labeling

Preparations (both active and placebo) will be packaged in white HDPE (high density polyethylene plastic) vials topped with cotton balls.

8.4 Supply of Study Drug at the Site

8.4.1 Dosage/Dosage Regimen

Participants will take the study drug (either 3 mg melatonin, 6 mg melatonin or placebo) at night one hour before bedtime (approximately 21:00 hours).

8.4.2 Dispensing

A medication bottle will be given to participants at the enrollment visit for the single blind placebo phase. For those eligible to continue to the 8-week double blind phase, the pharmacy will ship the final study drug bottle to the participant's home.

8.4.3 Administration Instructions

Participants will take the study drug (either 3 mg melatonin, 6 mg melatonin or placebo) orally at night one hour before bedtime (approximately 21:00 hours).

8.4.4 Storage

Pharmacy storage – the pharmacy is capable of monitoring temperature ranges via digital USB data loggers that can track humidity, temperature, and dew point. These reports can be regularly downloaded, printed for record, and monitored for consistency.

Storage at participants' homes—Study drug should be stored at the participants' homes at room temperature, 15 to 30°C (59 to 86°F). High humidity and high temperatures should be avoided.

8.5 Study Drug Accountability

An accurate and current accounting of the dispensing and return of study drug for each subject will be maintained on an ongoing basis by a member of the study site staff. The number of study drug dispensed and returned by the subject will be recorded on the Investigational Drug Accountability Record. The PI will verify these documents throughout the course of the study. In the daily headache diary, participants will also self-report whether they took the study drug that evening. Staff will be able to monitor this real time.

8.6 Measures of Treatment Compliance

Subjects will be asked to complete a daily headache diary and will be asked whether they took the study medication that evening. The diaries will be monitored by study staff. Also, a manual pill count will be performed after each phase of the study.

9 STUDY PROCEDURES AND GUIDELINES

Prior to conducting any study-related activities, written informed consent and the Health Insurance Portability and Accountability Act (HIPAA) authorization must be signed and dated by the subject's parent/guardian. Assent from the participant must also be obtained prior to conducting any study-related activities.

9.1 Clinical Assessments

9.1.1 Concomitant Medications

All concomitant medication and concurrent therapies will be documented at screening. Dose, route, unit frequency of administration, and indication for administration and dates of medication will be captured.

9.1.2 Demographics

Demographic information (date of birth, gender, race) will be recorded at screening.

9.1.3 Medical History

Relevant medical history, including history of current disease, other pertinent respiratory history, and information regarding underlying diseases will be recorded at screening.

9.1.4 Physical Examination

A physical examination will be performed by either an investigator or a sub-investigator at the screening visit.

9.1.5 Vital Signs

Body temperature, blood pressure, and pulse will be performed after resting for 5 minutes.

9.1.6 Adverse Events

Information regarding occurrence of adverse events will be captured throughout the study. Duration (start and stop dates and times), severity/grade, outcome, treatment and relation to study drug will be recorded on the case report form (CRF).

9.2 Clinical Laboratory Measurements

9.2.1 Pregnancy Test

A urine pregnancy test will be obtained from female subjects who are of childbearing age and have had their first menstrual period, prior to their participation in the study.

10 EVALUATIONS BY VISIT

10.1 Visit 1 (Screening and Enrollment, Day 1)

We will do a one-time enrollment visit at either UCSF or UCLA.

Consent/assent: At the start of an enrollment visit, potential subjects and their parent/guardian will be told about the study by a study investigator and/or study coordinator and will be provided with an informed consent document to review. For 12-17 year-olds, the informed consent document is addressed to the adolescent and is to be signed by both the adolescent and their parent/guardian. For 10-11 year-olds, the parent will sign the consent form and the participant will be provided with a simplified assent document. For this group the participant's assent will be documented by a study team member. Participants and parents/guardians will be given the opportunity to ask questions and have them answered to their satisfaction before deciding whether to participate. Consent and HIPPA can be signed with paper/pen or via DocuSign.

Enrollment visit data:

The enrollment visit data will be entered directly into the study database during the enrollment visit. Demographic and logistical information will be collected including name, age, sex, race/ethnicity, shipping address, participant smartphone number, parent smartphone number, and best times for follow-up calls. A pediatric headache neurologist will review the headache history to ensure the participant meets ICHD criteria for migraine with or without aura and will review the current medication list and past medical history. We will measure weight, blood pressure, pulse, and respiratory rate. There will be a general medical examination and a neurologic examination. Girls who have had their first period will undergo a urine pregnancy test. Baseline assessment of the PedMIDAS score and CASQ score will be assessed. Participants will be taught how to use the headache diary on their smartphone. They will be given the study medication for the single-blind placebo treatment phase and instructed to take study medication 1 hour before bedtime.

10.2 8-week single-blind placebo treatment phase (Weeks 1-8):

Participants will take the study medication nightly and complete a headache diary nightly. A text message will be sent from the study database each evening to remind them to do

these two tasks, and to provide a link to their headache diary. If they do not complete the headache diary, a reminder text will be sent the next morning. If they do not complete the headache diary for three days in a row, a study staff member will call to check in and remind them to do it and answer any questions. There will be a scheduled check in call at the four-week mark and again at the 8-week mark. If they provide headache diary data on $\geq 80\%$ of days in each 28-day period, they will receive a \$5 gift card each month. Once they have completed the 8-weeks of placebo treatment, they will return their study medication in a self-addressed envelope via FedEx.

10.3 Assessment of randomization eligibility (Day 57):

If the participant meets randomization criteria, the study pharmacy (Safeway) will be notified by study staff and the study pharmacy will review the randomization scheme to assign treatment and will enter this data into the study database. The study medication will be shipped to the participant's shipping address via FedEx.

Study staff will track the shipment via FedEx's tracking number on their website. Once the package shows as delivered, study staff will enter this information into the study database and a text message will be sent to the parent's smartphone asking them to confirm receipt of the study medication. The date the parent confirms receipt of the study medication will be day 1 of the randomized treatment phase.

10.4 8-week randomized treatment phase (Weeks 9-16):

Participants will take the study medication nightly and complete a headache diary nightly. A text message will be sent from the study database each evening at 9:00 PM to remind them to do these two tasks, and to provide a link to their headache diary. If they do not complete the headache diary, a reminder text will be sent the next morning. If they do not complete the headache diary for three days in a row, a study staff member will call to check in and remind them to do it and answer any questions. There will be a scheduled check in call at the four-week mark and again at the 8-week mark. If they provide headache diary data on $\geq 80\%$ of days in each 28-day period, they will receive a \$5 gift card each month. Once they have completed the 8-weeks of treatment, they will return their study medication in a self-addressed envelope via FedEx.

10.5 Study completion (Day 113):

At the end of the 8-week randomized treatment phase there will be a study completion phone visit. We will again assess the PedMIDAS and CASQ scores. We will query for adverse events, and will solicit participant and parent feedback on the study design. We will remind participants to mail back the study medication bottle using the self-addressed FedEx envelope, and once this is received we will perform both a manual pill count and compare to the self-report count in their diary.

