14.3 Analysis of Primary Endpoint

Primary outcome: Number of migraine/migrainous days in the 5th-8th weeks of randomized treatment between melatonin (combined 6 mg+3mg) vs. placebo. We will control for baseline migraine/migrainous day frequency in the 5-8th week of the single-blind treatment phase and use an ANCOVA analysis.

Definition of migraine/migrainous day:

- 1) Patient had a moderate or severe headache and took a migraine-specific medication (triptan or ergot)
- 2) Patient had a moderate or severe headache; headache lasted for at least 2 hours, and
 - a. At least one of the following was present (throbbing quality, movement sensitivity, or unilateral/bilateral location) AND
 - b. At least one of the following was also present (photophobia, phonophobia, nausea or vomiting)

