14.4 Analysis of Secondary Endpoints

Secondary outcome measures will include $\geq 50\%$ responder rates, tolerability (as measured by CASQ scores), and need for use of acute headache medications. Safety and tolerability data will be summarized by treatment group. Adverse event rates will be coded by body system. Adverse events will be tabulated by treatment group and will include the number of patients for whom the event occurred, the rate of occurrence, and the severity and relationship to study drug.

Secondary outcomes:

(We will control for the baseline level of these outcomes in all of these analyses)

Effectiveness secondary outcomes:

1. Number of migraine/migrainous days in the 5th-8th weeks of randomized treatment between **melatonin 3 mg vs. placebo**.

2. Number of migraine/migrainous days in the 5th-8th weeks of randomized treatment between **melatonin 6 mg vs. placebo**.
3. Number of migraine/migrainous days in the 5th-8th weeks of randomized treatment between **melatonin 3 mg vs. 6 mg**.
4. Mean headache days in 5th-8th randomized phase in melatonin (combined) vs. placebo, (followed by melatonin 3 mg vs. placebo, melatonin 6 mg vs. placebo, and melatonin 3 mg vs. melatonin 6 mg using t-tests).
5. Mean acute medication use days in 5th-8th randomized phase in melatonin (combined) vs. placebo, (followed by melatonin 3 mg vs. placebo, melatonin 6 mg vs. placebo, and melatonin 3 mg vs. melatonin 6 mg using t-tests).
6. Mean PedMIDAS score (continuous) in 5th-8th randomized phase in melatonin (combined) vs. placebo, (followed by melatonin 3 mg vs. placebo, melatonin 6 mg vs. placebo, and melatonin 3 mg vs. melatonin 6 mg using t-tests).
7. $\geq 50\%$ responder rate in 5th-8th randomized phase in melatonin (combined) vs. placebo (Chi-square or Fisher's exact (if needed), (followed by melatonin 3 mg vs. placebo, melatonin 6 mg vs. placebo, and melatonin 3 mg vs. melatonin 6 mg using Chi-square (or Fisher's exact)).

Safety outcomes:

1. Proportion with adverse events between groups
 - a. Proportion with serious adverse events between groups
 - b. Proportion of adverse events thought to be related to the study treatment
2. Mean Sleepiness score in 5th-8th randomized phase in melatonin (combined) vs. placebo, (followed by melatonin 3 mg vs. placebo, melatonin 6 mg vs. placebo, and melatonin 3 mg vs. melatonin 6 mg using t-tests).

Trial design assessment outcome:

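### PedMIDAS and CASQ are not repeated after the placebo run-in; giving both at the existing 8-week call is a cheap way to a more precise baseline adjustment

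*Combined protocol and SAP*

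**What the plan says.** - **Day 1 (section 10.1).** "Baseline assessment of the PedMIDAS score and CASQ score will be assessed". Run-in placebo is handed out at the same visit: "They will be given the study medication for the single-blind placebo treatment phase and instructed to take study medication 1 hour before bedtime".
- **Weeks 1-8 (section 10.2).** "There will be a scheduled check in call at the four-week mark and again at the 8-week mark". Neither questionnaire is among the procedures listed.
- **Day 57 (section 10.3).** "If the participant meets randomization criteria, the study pharmacy (Safeway) will be notified by study staff", which then assigns treatment and ships it. No questionnaire is listed here either. The randomised phase begins later: "The date the parent confirms receipt of the study medication will be day 1 of the randomized treatment phase".
- **Day 113 (section 10.5).** At the completion phone visit, "We will again assess the PedMIDAS and CASQ scores".
- **Analysis of secondary outcomes (section 14.4).** "We will control for the baseline level of these outcomes in all of these analyses". The time point that counts as baseline is not defined.
- **Analysis of the primary endpoint (section 14.3).** "We will control for baseline migraine/migrainous day frequency in the 5-8th week of the single-blind treatment phase".
- **Appendix 1.** There is no row for PedMIDAS or CASQ at any visit.

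**The concern.** For its main outcome the plan takes the end of the run-in as the reference state. Both the randomisation criteria and the primary covariate use weeks 5-8 of single-blind placebo. The diary-based secondary outcomes (headache days, acute-medication days) can be adjusted over the same window. PedMIDAS and CASQ cannot, because their only pre-randomisation value precedes the run-in. The single sentence on baseline control in section 14.4 therefore covers two different baselines, about 8 weeks apart, without saying so.

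A covariate measured further from the outcome usually predicts it less well, so adjusting for it removes less noise. Section 2.1 expects a high placebo response in paediatric migraine trials, so disability may well move between Day 1 and week 8. At stake is the precision of the disability outcome and of the scored measure of daytime sleepiness, which section 2.1 names as essentially the only risk reported with these doses. A pre-randomisation score that was not collected cannot be recovered later.

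**Working it through.** **1. Timing, from the day numbers in section 10**

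- Baseline to randomisation check: Day 57 − Day 1 = 56 days.
- Baseline to outcome: Day 113 − Day 1 = 112 days.
- Both are nominal. Shipping time until the parent confirms receipt adds to the second, and Appendix 1 allows a visit window.
- The primary covariate covers weeks 5-8 of the run-in, that is, the 28 days before the randomisation check.

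**2. The plan's own sample-size figure**

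Section 14.6 gives 42 per arm for a difference of 1.1 days and SD 1.8. Alpha and power are not stated; two-sided 5% and 80% are assumed. Then n = 2 × (1.960 + 0.842)² × 1.8² / 1.1² = 42.03, which reproduces 42. The calculation concerns migraine/migrainous days only and uses no baseline correlation, so nothing in this point changes it.

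**3. Precision under an adjusted analysis**

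With baseline-outcome correlation r, the residual variance of an ANCOVA is proportional to 1 − r². The variance with a Day 1 covariate relative to a week-8 covariate is

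R = (1 − r₁²) / (1 − r₈²).

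The same factor R is the relative number of participants needed for equal precision, and √R is the ratio of standard errors. The documents give no correlation for either questionnaire. Assumed ranges: r₁ from 0.3 to 0.5 and r₈ from 0.5 to 0.7. R falls as r₁ rises and rises with r₈, so the corners of the grid give its extremes. The last column takes a comparison that would have 80% power with the week-8 covariate and computes Φ(2.802/√R − 1.960).

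| r₁ (Day 1) | r₈ (week 8) | R | √R | Power with Day 1 covariate |
|---|---|---|---|---|
| 0.5 | 0.5 | 0.75/0.75 = 1.00 | 1.00 | 80% |
| 0.3 | 0.5 | 0.91/0.75 = 1.21 | 1.10 | 72% |
| 0.5 | 0.7 | 0.75/0.51 = 1.47 | 1.21 | 64% |
| 0.3 | 0.7 | 0.91/0.51 = 1.78 | 1.34 | 55% |

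The gain from a week-8 baseline thus runs from 0% to 78% more participants in effect. If the two correlations are equal, nothing is gained.

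**4. Which comparisons are affected**

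- *PedMIDAS:* it is in the list of secondary outcomes to which the adjustment sentence applies, in the synopsis and in section 14.4.
- *CASQ:* section 14.4 names it among the secondary outcome measures but lists the sleepiness score under safety outcomes. The synopsis puts sleepiness under other evaluations, outside the list that carries the adjustment sentence. Section 5.2 lists it as a secondary efficacy endpoint.
- *Pairwise comparisons:* section 14.4 names t-tests for both scores. An ordinary t-test uses no covariate, so the timing of baseline would not matter there unless the promise to adjust prevails.

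**The case against.** The strongest reply is that nothing here is invalid. The Day 1 score is taken before randomisation, so adjusting for it leaves the randomised comparison unbiased. A reader might infer from the early baseline that the treatment effect on disability or sleepiness is distorted; the documents do not support that. This part of the objection stands in full.

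A reader might also infer that the reported effect will mix run-in placebo response with drug effect. That would concern a change from Day 1, and none is planned for these scores. Sections 5.2 and 14.4 compare mean scores between groups. The only change endpoint, item 4 of section 5.2, is for migraine/migrainous days and already starts from run-in weeks 5-8. Even for a change score, run-in response precedes allocation and is balanced between arms in expectation.

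Nor do the documents say that the run-in exists to remove placebo response. The function they give it is eligibility: migraine-day count and diary compliance. For CASQ, nothing in the documents suggests that scores shift on placebo. They also give no recall period for either instrument, so they do not establish that a Visit 3 score would reflect only the run-in state. Adding the run-in diary count as a covariate might recover some of the precision for PedMIDAS.

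The missing rows in Appendix 1 are a documentation gap, since sections 10.1 and 10.5 state both administrations plainly.

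What survives is narrower: the plan promises adjustment, leaves baseline undefined, and omits a later measurement that it could obtain almost for free. The 8-week call exists, and the protocol already gives both questionnaires by telephone at completion. A telephone baseline would match that mode, which the in-person Day 1 visit does not.

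**Conclusion.** The point holds as a cheap improvement in precision and not as a flaw in validity. The only pre-randomisation PedMIDAS and CASQ scores predate the whole run-in, while the primary endpoint uses its last four weeks. The effect is confined to one secondary outcome and to the sleepiness measure, for which adjustment is itself less clearly specified.

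The size cannot be derived from the documents. Under the assumed correlations the residual variance is 1.00 to 1.78 times as large with the Day 1 covariate, and the range includes no loss at all. A reader might take the upper figure as a shortfall in sample size. It is not one, because the plan sets no power target for these outcomes. The figures also presuppose that a covariate-adjusted analysis is actually run. The expectation of some gain rests on the general tendency of a score nearer the outcome to predict it better, not on data in the plan.

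**What to change.** - Give PedMIDAS and CASQ at the existing 8-week call (Visit 3), completed before the pharmacy is notified and treatment is assigned.
- Keep the Day 1 values to describe participants at entry.
- In section 14.4, name the Visit 3 score as the baseline covariate for PedMIDAS and CASQ, and say explicitly whether the adjustment applies to CASQ.
- Add both questionnaires to Appendix 1 at Visits 1, 3 and 5. The column heading for Visit 5 repeats that of Visit 4; it is taken here to be the completion call.

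The cost is a few minutes of participant and staff time on a call that already takes place, and a small protocol edit. If data collection cannot change, the minimum is to define the baseline for these two scores as the Day 1 value in section 14.4 and to complete Appendix 1 at Visits 1 and 5.

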11 ADVERSE EXPERIENCE REPORTING AND DOCUMENTATION

11.1 Adverse Events

An adverse event (AE) is any untoward medical occurrence in a clinical investigation of a patient administered a pharmaceutical product and that does not necessarily have a causal relationship with the treatment. An AE is therefore any unfavorable and unintended sign (including an abnormal laboratory finding), symptom or disease temporally associated with the administration of an investigational product, whether or not related to that investigational product. An unexpected AE is one of a type not identified in nature, severity, or frequency or of greater severity or frequency than expected.

The study team will probe, via discussion with the subject, for the occurrence of AEs during each subject visit and record the information in the site's source documents.

Adverse events will be recorded in the patient CRF. Adverse events will be described by duration (start and stop dates and times), severity, outcome, treatment and relation to study drug, or if unrelated, the cause.

AE Severity

The National Cancer Institute's Common Terminology Criteria for Adverse Events (CTCAE) Version 3.0 should be used to assess and grade AE severity, including laboratory abnormalities judged to be clinically significant. The modified criteria can be found in the study manual. If the experience is not covered in the modified criteria, the guidelines shown in Table 1 below should be used to grade severity. It should be pointed out that the term "severe" is a measure of intensity and that a severe AE is not necessarily serious.

Table 1. AE Severity Grading

| Severity (Toxicity Grade) | Description |
|---------------------------|---|
| Mild (1) | Transient or mild discomfort; no limitation in activity; no medical intervention or therapy required. The subject may be aware of the sign or symptom but tolerates it reasonably well. |
| Moderate (2) | Mild to moderate limitation in activity, no or minimal medical intervention/therapy required. |
| Severe (3) | Marked limitation in activity, medical intervention/therapy required, hospitalizations possible. |
| Life-threatening (4) | The subject is at risk of death due to the adverse experience as it occurred. This does not refer to an experience that hypothetically might have caused death if it were more severe. |

AE Relationship to Study Drug

The relationship of an AE to the study drug should be assessed using the following the guidelines in Table 2.

Table 2. AE Relationship to Study Drug

| Relationship to Drug | Comment |
|----------------------|---|
| Definitely | Previously known toxicity of agent; or an event that follows a reasonable temporal sequence from administration of the drug; that follows a known or expected response pattern to the suspected drug; that is confirmed by stopping or reducing the dosage of the drug; and that is not explained by any other reasonable hypothesis. |
| Probably | An event that follows a reasonable temporal sequence from administration of the drug; that follows a known or expected response pattern to the suspected drug; that is confirmed by stopping or reducing the dosage of the drug; and that is unlikely to be explained by the known characteristics of the subject's clinical state or by other interventions. |
| Possibly | An event that follows a reasonable temporal sequence from administration of the drug; that follows a known or expected response pattern to that suspected drug; but that could readily have been produced by a number of other factors. |
| Unrelated | An event that can be determined with certainty to have no relationship to the study drug. |

